V2.0	14Mar2018	
Final SAP was amended after clinical database lock updated to version 2.0. SAP section 1.Sample size for the Target mTNBC Population has been revised and updated to 108. SAP section 3.4.Sample size for patients who received at least 2 lines of prior standard chemotherapy for metastatic disease (ie, excluding hormonal or other investigational treatment) updated to 94. SAP section 3.4.Per-Protocol Population definition has been reworded. SAP section 4.3.Data listing for the efficacy population has been updated to 108. SAP section 4.1.Patients Disposition category screened/entered into the study has been excluded. SAP section 5.1.A separate listing of patients registered but did not receive study drug has been excluded. SAP section 5.1.New text has been added to Percentage of patients with dose reduction. SAP section 5.5.Planned dose intensity definition has been updated. SAP section 5.5.Response assessment dates derivation has been corrected. SAP section 6.Objective response rate definition has been reworded. SAP section 6.2.Clinical benefit rate definition has been updated and corrected. SAP section 6.3.Guidelines and specification for Progression Assessment and Censoring for Analysis of PFS has been updated. SAP section 6.4.Duration of Response definition has been updated. SAP section 6.6.Sensitivity analyses text has been modified. SAP section 6.9.Treatment-related Grade 3 or higher AEs by SOC and PT was removed and on treatment deaths definition has been updated. SAP section 7.1.Lab baseline definition has been updated. SAP section 7.3.

		
• New text has been added for the eDISH figures, defining the Horizontal and Vertical lines for 3xULN and 2XULN. SAP section 7.3.• Informed Consent major protocol violation category has been removed. SAP section 8.• New text has been added to clarify derivation of Radiation during treatment violation category under prohibited medications category of major protocol violation. SAP section 8.• Best Overall Response with Confirmation of CR and PR Required table has been updated for the patients missing subsequent response. Appendix 12.
V3.0	01Feb2019	
• Added analyses populations other than the Target mTNBC Population based on cancer histology and associated efficacy and safety analyses.• Added additional subgroup analyses for selected efficacy and safety endpoints.• Added safety analyses and definitions of AE of special interest.• Added some additional safety analyses for the Overall Safety Population.• Dose intensity and relative dose intensity definitions are clarified and updated.• The study drug name sacituzumab govitecan is added to the SAP. Where IMMU-132 is referred to, in keeping consistent with the Protocol, is identical to sacituzumab govitecan that may be used in other documents.• Added operational dates and characteristics such as data planned data cut-off date, last patient enrolment date and total number of subjects enrolled for final CSR analyses.• Changed the programming spec for swimmer plot.• CCI [REDACTED]• Moved data handling rules of missing dates from the SAP into separate documentation.

TABLE OF CONTENTS

1.	INTRODUCTION	9
2.	STUDY OBJECTIVES	10
2.1.	Primary Objective.....	10
2.2.	Secondary Objectives	10
3.	INVESTIGATIONAL PLAN.....	11
3.1.	Overall Study Design and Plan.....	11
3.2.	Phase I Dose-Escalation	12
3.3.	Phase II	12
CCI	[REDACTED]	
4.	ANALYSIS POPULATIONS	14
4.1.	Efficacy Populations	15
4.2.	Safety Populations	15
4.3.	Per-Protocol Population.....	16
4.4.	Analyses Population Overview.....	16
5.	STATISTICAL ANALYSES	19
5.1.	Patient Disposition.....	19
5.2.	Demographics and Baseline Characteristics.....	19
5.2.1.	Demographics	19
5.2.2.	Baseline Disease Characteristics	20
5.3.	Prior Anticancer Therapy	20
5.4.	Concomitant Medications and Medical History	20
5.4.1.	Medical History	20
5.4.2.	Concomitant Medications	20
5.5.	Exposure to Study Drug and Compliance	21
6.	EFFICACY ANALYSIS	23
6.1.	Best Overall Response.....	23
6.2.	Objective Response Rate	23
6.3.	Clinical Benefit Rate.....	23
6.4.	Progression-Free Survival	24
6.5.	Overall Survival.....	26

6.6.	Duration of Response	26
6.7.	Time to Response	27
6.8.	Other Analyses Related to Efficacy.....	27
6.9.	Sensitivity Analyses.....	28
CCI		
7.	SAFETY ANALYSIS	30
7.1.	Adverse Events	30
7.2.	Death.....	32
7.3.	Clinical Laboratory Evaluations	32
7.3.1.	Pregnancy Tests	33
7.4.	Physical Examination	34
7.5.	Vital Signs	34
7.6.	Electrocardiograms	34
8.	MAJOR PROTOCOL DEVIATIONS	35
9.	INTERIM ANALYSIS	36
10.	METHODS FOR HANDLING MISSING DATA.....	37
11.	CHANGES TO THE PLANNED ANALYSES OR THE STATISTICAL ANALYSIS SECTION FROM THE PROTOCOL	38
12.	APPENDIX.....	39

LIST OF ABBREVIATIONS AND DEFINITION OF TERMS

Abbreviation	Definition
ADC	Antibody-drug conjugate
AE	Adverse event
ALT	Alanine aminotransferase
ASCO	American Society of Clinical Oncology
AST	Aspartate aminotransferase
ATC	Anatomical Therapeutic Chemical
CCI	[REDACTED]
BMI	Body mass index
BOR	Best overall response
CAP	College of American Pathologists
CR	Complete response
CRF	Case report form
CT	Computed tomography
CTCAE	Common Terminology for Adverse Events
DILI	Drug-induced liver injury
DOOR	Duration of response
ECG	Electrocardiogram
ECOG	Eastern Cooperative Oncology Group
eDISH	Evaluation of drug-induced serious hepatotoxicity
FDA	Food and Drug Administration
HAHA	Human anti-human antibody
HR	Heart rate
ICR	Independent central review
MedDRA	Medical Dictionary for Regulatory Activities
MRI	Magnetic resonance imaging
mTNBC	Metastatic Triple-Negative Breast Cancer
NCI	National Cancer Institute
NSCLC	Non-small cell lung cancer
ORR	Objective response rate
OS	Overall survival
PD	Progressive disease
PFS	Progression-free survival

Abbreviation	Definition
PK	Pharmacokinetic
popPK	Population Pharmacokinetics
PP	Per-protocol
PR	Partial response
PT	Preferred term
RECIST	Response Evaluation Criteria in Solid Tumors
SAE	Serious adverse event
SAP	Statistical analysis plan
SCLC	Small cell lung cancer
SD	Stable disease
SOC	System organ class
TBL	Total bilirubin level
TEAE	Treatment-emergent adverse event
TNBC	Triple Negative Breast Cancer
TTR	Time to response
UC	Urothelial Cancer
UGT1A1	Uridine diphosphate glucuronosyltransferase 1A1
ULN	Upper limit of normal
US	United States
WHO	World Health Organization

[figure not shown]
1. INTRODUCTION

This document is the Statistical Analysis Plan (SAP) for Protocol IMMU-132-01 “A Phase I/II Study of IMMU-132 (hRS7-SN38 Antibody Drug Conjugate) in Patients with Epithelial Cancer,” which was issued on 24 April 2017 (includes Amendments #1 through #11).

This SAP provides a comprehensive and detailed description of the strategy, rationale, and statistical techniques used to evaluate the specified efficacy and safety endpoints.

Safety and efficacy data will be presented separately for the metastatic Triple-Negative Breast Cancer (mTNBC) Target Population, metastatic non-triple-negative Breast Cancer (mBC) population and metastatic Urothelial Cancer (mUC) including urinary bladder as specifically defined in [Section 4, Analyses Population](#). In addition, safety data will also be presented on all patients, irrespective of tumor type or IMMU-132 dose received; this population will for the remainder of the SAP be referred to as the Overall Safety Population. Whereas patients populations with cancer type Small-cell lung cancer (SCLC), Non-small-cell lung cancer (NSCLC), Colorectal (CRC), Esophageal cancer (EGC), Endometrial cancer (EMC), and Pancreatic ductal adenocarcinoma (PDC) will be analyzed separately only for the selected efficacy endpoints.

CCI

Subsequently, the SAP is amended (Version 3.0) to include efficacy and safety analyses for patient populations (as defined by underlying malignancy) other than the Target mTNBC Population, and additional safety analyses for the Overall Safety Population, to be based on data from final database lock (DBL) with planned data cut-off date of 1 March 2019, in support of the clinical study report (CSR). Separate pharmacokinetic (PK) analysis, popPK and immunogenicity plans will detail the PK, popPK and immunogenicity analyses.

2. STUDY OBJECTIVES

This is a first-in-man clinical study with the antibody-drug conjugate (ADC), IMMU-132, which uses the humanized antibody hRS7 to deliver the topoisomerase I inhibitor, SN-38, directly to Trop-2-expressing epithelial tumors. The study has been conducted in 2 Phases. Dose escalation in Phase I was designed to determine a maximum acceptable dose and to select cancer types for further study in the Phase II expansion cohorts. Phase II continued enrollment with dose levels and cancers selected based upon Phase I results and preliminary efficacy results.

2.1. Primary Objective

The primary objective in Phase I is to identify the maximum acceptable dose and evaluate the safety and tolerability of IMMU-132 as a single agent administered in 3-week treatment cycles, in previously treated patients with advanced epithelial cancers. The primary objective in Phase II is the evaluation of the safety and efficacy of IMMU-132 administered in 3-week treatment cycles, at a dose selected in Phase I.

2.2. Secondary Objectives

In Phase I, the secondary objectives are to obtain initial data concerning PK, immunogenicity, and efficacy with this dosing regimen. In Phase II, secondary objectives also include PK and immunogenicity.

3. INVESTIGATIONAL PLAN

3.1. Overall Study Design and Plan

IMMU-132-01 is a Phase I/II, open-label, basket design study of IMMU-132 in adult patients with epithelial cancers expressing Trop-2. The allowed cancer types include ovarian, endometrial, cervical, breast (Triple-Negative Breast Cancer [TNBC] and non-TNBC), prostate (hormone refractory), lung (non-small cell and small-cell lung [NSCLC and SCLC], head and neck (squamous cell), esophageal, gastric, hepatocellular, renal (clear cell), thyroid, glioblastoma multiforme, colorectal, pancreatic, and urothelial cancers (UC). Eligible patients were required to have metastatic (Stage IV) disease at the time of study entry (except for glioblastoma multiforme) and be refractory to or have relapsed after at least 1 prior standard therapeutic regimen for their disease. All patients received IMMU-132 administered IV as a single agent in 3-week treatment cycles (Days 1 and 8 of 21-day cycles). Patients were to continue treatment until disease progression requiring discontinuation of treatment or unacceptable toxicity. A protocol-defined dose reduction scheme was in place to manage patients with selected AEs.

The primary objective of Phase I is to evaluate the safety and tolerability of IMMU-132 in patients with advanced epithelial cancers, using a dose escalation design to determine the maximum acceptable dose. The secondary objective of Phase I is to evaluate the PK, immunogenicity, and preliminary efficacy of IMMU-132. The primary objective of Phase II is the evaluation of the safety and efficacy of IMMU-132 at a dose selected in Phase I, while the secondary objectives of Phase II also include evaluation of PK and immunogenicity.

Screening/baseline procedures include patient history, physical examination with vital signs and performance status evaluation, local histology/pathology review to confirm 1 of the epithelial cancers listed above, safety laboratory assessments, and electrocardiogram (ECG). Tumor imaging was performed using contrast enhanced computed tomography (CT) or magnetic resonance imaging (MRI). Baseline imaging was obtained within 4 weeks of study entry. Blood/samples were collected to test for human anti-human antibody (HAHA), and uridine diphosphate glucuronosyltransferase 1A1 (UGT1A1) genotype CCI

During the study, imaging was performed at baseline (ie, within 4 weeks of study entry) and thereafter in 8 weekly intervals from the start of treatment onwards, with confirmatory CT/MRI scans obtained 4 to 6 weeks after an initial partial response (PR) or complete response (CR), until permanent treatment discontinuation. Response assessment was performed according to Response Evaluation Criteria in Solid Tumors (RECIST) version 1.1. Response assessment was performed locally, but independent central review (ICR) of the tumor scans was additionally obtained for mTNBC patients who had at least 2 prior therapies for metastatic disease, were being treated at the 10 mg/kg dose level, and whose local scans demonstrated at least 20% decrease. ICR of tumor scans was performed by Intrinsic Imaging (Bolton, Massachusetts; San Antonio, Texas, US). The details of the independent review were provided in an imaging charter for the study.

After treatment discontinuation, patients were to be followed until resolution or stabilization of any treatment-related AEs. All patients were followed for survival every month, which may be by telephone with patient or caregiver.

CCI

The safety of patients is assessed based on occurrence of AEs, clinical laboratory assessments, vital signs, and ECGs.

3.2. Phase I Dose-Escalation

Phase I dose-escalation used a standard 3+3 dose escalation design. Three to 6 patients per cohort were to be enrolled in up to 4 planned dose levels, for a planned total number of 24 patients. Based on preclinical studies, 8 mg/kg was selected as the starting dose.

3.3. Phase II

In Phase II, after initially enrolled patients were evaluated in each cancer indication selected by the Sponsor in up to 2 dose levels to provide additional safety and efficacy data, indications showing a promising tumor response were considered adequate evidence of activity for further clinical development, which included TNBC, NSCLC, SCLC and UC. After initial review of patients treated at both IMMU-132 doses of 8 and 10 mg/kg, 10 mg/kg was selected for further clinical development. This dose has been received by the majority of patients in this study, including the majority of patients with mTNBC.

CCI

The enrollment of patients of the target mTNBC population was stopped on 14 February 2017 since the enrollment goals were met after a total of 148 mTNBC patients had been entered, but the enrollment of patients in other cancer indications continued. Subsequently, in June 2017, the Sponsor notified the sites of the decision to stop further enrollment of patients into the study, and the last patient enrolled occurred on 22 June 2017.

CCI

CCI

CCI

CCI

CCI

4. ANALYSIS POPULATIONS

Given that this study was conducted as a Phase I/Phase II and included a diverse population comprised of patients with different tumor types, it is necessary to define specific patient populations. The following sections outline the populations to be included for the evaluation of efficacy and safety. The patient populations to be used are:

- Target mTNBC Population: Patients with relapsed/refractory mTNBC who have received at least 2 prior therapies for metastatic disease and who received IMMU-132 at a dose of 10 mg/kg.
- Per-Protocol (PP) Population (specific to the Target mTNBC Population): This will include patients of the Target mTNBC Population who received at least 1 complete cycle of IMMU-132 and had data available from at least 1 response assessment.
- Overall Safety Population: This will include all patients who received at least 1 dose of IMMU-132, irrespective of dose, tumor type, or number of prior therapies.

At the time of final SAP (version 3.0), the following patient populations are added for safety and efficacy analyses:

- Metastatic, non-triple-negative breast cancer (mBC) Population: This will include all patients with hormone receptor-positive/human epidermal growth factor receptor 2-negative (HR+/HER2-) metastatic breast cancer (mBC) who progressed on at least 1 prior hormonal therapy in the metastatic setting and who received at least 1 dose of IMMU-132 at a dose of 10 mg/kg.
- Metastatic Urothelial cancer including urinary bladder (mUC) Population: This will include all mUC patients who had relapsed after or were refractory to at least 1 prior standard therapeutic regimen and who received at least 1 dose of IMMU-132 at a dose of 10 mg/kg.

And the following patient populations are added for limited efficacy analyses:

- Small-cell lung cancer (SCLC) Population: This will include all SCLC patients as enrolled in the study in accordance with the eligibility criteria and who received at least 1 dose of IMMU-132.
- Non-small-cell lung cancer (NSCLC) Population: This will include all NSCLC patients as enrolled in the study in accordance with the eligibility criteria and who received at least 1 dose of IMMU-132.
- Colorectal (CRC) Population: This will include all CRC patients as enrolled in the study in accordance with the eligibility criteria and who received at least 1 dose of IMMU-132.
- Esophageal cancer (EGC) Population: This will include all EGC patients as enrolled in the study in accordance with the eligibility criteria and who received at least 1 dose of IMMU-132.
- Endometrial cancer (EMC) Population: This will include all EMC patients as enrolled in the study in accordance with the eligibility criteria and who received at least 1 dose of IMMU-132.

- Pancreatic ductal adenocarcinoma (PDC) Population: This will include all PDC patients as enrolled in the study in accordance with the eligibility criteria and who received at least 1 dose of IMMU-132.

For the mTNBC target population of 108 patients, it was ensured that all patients had a minimum of 4 months follow-up. This allowed to include at least 2 post-baseline assessments (except for patients who died or discontinued study treatment prior to their second post-baseline scan).

CCI

At the time of final analyses, because of the additional enrollment up until 22 June 2017, the Overall Safety Population increased to approximately 495.

CCI

Subsequently, for the final data analyses to support CSR, the targeted data cut-off date is planned on 01 March 2019. If different, the actual data cut-off will be stated in the CSR. The cut-off date applies to both the Overall Safety Population and individual cancer populations.

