In the event of treatment termination due to unacceptable toxicity, the patient will continue on study follow up until there is documentation of progression of disease, at which time an end-of-study evaluation will be performed, with additional follow-up only required until resolution or stabilization of any treatment-related toxicity.

Long-term follow-up will continue in patients with stable disease or an objective response with evaluations performed every 3 months for up to 2 years or until progression of disease or initiation of other treatment. All patients will be followed for survival every month, which may be by telephone, but no longer than 2 years from final study evaluation.

Patients continuing to benefit from treatment at time of study closure may be eligible to enroll in a rollover study, so they may continue to receive treatment.

(See study calendar below for detailed schedule of procedures)

Population

Males or non-pregnant, non-lactating females \geq 18 years of age, able to give signed, written informed consent, may be eligible if they have documented epithelial cancer that involves any of the following tumor types: ovarian, cervical, endometrial, breast (triple-negative and other breast tumors), prostate (hormone refractory), lung (non-small-cell and small-cell), head and neck (squamous cell), esophageal, colorectal, gastric, pancreas, renal (clear cell), papillary thyroid, glioblastoma multiforme, urinary bladder (urothelial), and hepatocellular. Patients must have metastatic disease (except GBM) and have either relapsed after receiving or were refractory to at least one standard chemotherapy (or biological, targeted or hormonal) regimen for their disease.

CCI

CCI

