3. STUDY DESIGN

This is a Phase I/II, open-label study of IMMU-132 in previously treated patients with the following metastatic epithelial cancers:

- Gastric adenocarcinoma (GC)
- Esophageal cancer (EC)
- Hepatocellular carcinoma (HCC)
- Non-small cell lung cancer (NSCLC)
- Small-cell lung cancer (SCLC)
- Epithelial ovarian cancer (EOC)
- Cervical Cancer
- Papillary thyroid cancer
- Glioblastoma multiforme (GBM)
- Endometrial Cancer
- Triple-negative breast cancer (TNBC)
- Non-triple-negative breast cancer (mBC)
- Hormone-refractory prostate cancer (HRPC)
- Head and neck cancers- squamous cell (SCCHN)
- Renal cell carcinoma (clear cell) (RCC)
- Urothelial cancers, including urinary bladder cancer.

A table of approved or standard therapeutic regimens or regimens in documented clinical trials for each of these cancer types is included in **Appendix 1**. *Patients who have not received all approved or standard treatments for their cancer must be informed that these alternatives to receiving IMMU-132 are available prior to consenting to participate in this trial.*

In Phase II, up to 150 patients (assessable) in each of 5 cancer subtypes (TNBC, non-TNBC, NSCLC, SCLC, UC) and up to 56 patients (assessable) per other cancer types will be studied at the 10 mg/kg dose.

Based upon the Phase I results, the 8 mg/kg and 10 mg/kg dose levels were selected for further evaluation in Phase II, and subsequently the 10 mg/kg dose was selected for the ongoing Phase II study.

Baseline evaluations within 4 weeks of the scheduled start of treatment include patient history, physical examination with vital signs and performance evaluation, local histology review to confirm one of the epithelial cancers listed above, contrast-enhanced CT or MRI scans (chest, abdomen, pelvis with additional imaging of other involved areas), CBC (with differential and platelet count), routine serum chemistries, urinalysis, PT/PTT, EKG, and serum samples for human anti-human antibody (HAHA). **CCI**

CCI

CCI

CCI

A single whole-blood sample (purple or pink-topped tube, 2 mL) will be collected from each registered patient prior to receiving IMMU-132 for determination of *UGT1A1* or other *UGT1* genotype. This sample will be shipped to Sponsor who will perform this assay. The results are not used to establish eligibility but will be used for retrospective assessment of toxicity.

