4.1. Inclusion Criteria

- Male or female patients, ≥ 18 years of age, able to understand and give written informed consent.
- Histologically or cytologically confirmed epithelial cancer of one of the following types:
 - Gastric adenocarcinoma (GC)
 - Esophageal cancer (EC)
 - Hepatocellular carcinoma (HCC)
 - Non-small-cell lung cancer (NSCLC) CCI [REDACTED]
[REDACTED]
[REDACTED]
[REDACTED]
 - Small-cell lung cancer (SCLC)
 - Epithelial ovarian cancer (EOC)
 - Cervical Cancer
 - Endometrial Cancer
 - Triple-negative breast cancer CCI [REDACTED]
[REDACTED]
[REDACTED]
[REDACTED]
[REDACTED]
[REDACTED]
 - Non-triple-negative breast cancer
 - Papillary thyroid cancer (*excludes follicular, medullary, Hurthle cell, and anaplastic thyroid cancer*)
 - Glioblastoma multiforme (GBM)
 - Hormone-refractory prostate cancer (HRPC)
 - Head and neck cancers- squamous cell (SCCHN)
 - Renal cell cancer (clear cell) (RCC)
 - Urothelial cancer CCI [REDACTED]
[REDACTED]
[REDACTED]

CCI

- Stage IV (metastatic) disease (except for patients with GBM).
- Refractory to or relapsed after at least one prior standard therapeutic regimen.

(Appendix 1 lists approved or standard chemotherapeutic agents for each cancer type. Patients who have not received all approved or standard treatments for their cancer must be informed that these alternatives to receiving IMMU-132 are available prior to consenting to participate in this trial.)

- Adequate performance status (ECOG 0 or 1) ([Appendix 2](#)).
- Expected survival \geq 6 months.
- Measurable disease by CT or MRI.
- At least 2 weeks beyond treatment (chemotherapy, investigational drugs including small molecular inhibitors, endocrine therapy, immunotherapy and/or radiation therapy) or major surgery and recovered from all acute toxicities to Grade 1 or less (except alopecia).
- At least 2 weeks beyond high dose systemic corticosteroids (however, low dose corticosteroids < 20 mg prednisone or equivalent daily are permitted).
- Adequate hematology without ongoing transfusional support (hemoglobin > 9 g/dL, ANC $> 1,500$ per mm 3 , platelets $> 100,000$ per mm 3).
- Adequate renal and hepatic function (creatinine $\leq 2.0 \times$ IULN, bilirubin ≤ 1.5 IULN, AST and ALT $\leq 3.0 \times$ IULN or 5 x IULN if know liver metastases).
- Otherwise, all toxicity at study entry \leq Grade 1 by NCI CTCAE v4.0.

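### The SAP's non-triple-negative breast cancer (mBC) population is narrower than the Protocol's cohort of the same name, so treated non-TNBC patients outside it have no visible efficacy summary

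*SAP*

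**What the plan says.** **Protocol.** Section 3 lists the tumour type and attaches the abbreviation: "Non-triple-negative breast cancer (mBC"). Non-TNBC is one of five subtypes for which Phase II may study up to 150 assessable patients. The Population part of the synopsis describes eligible breast cancers as "breast (triple-negative and other breast tumors"). Section 4.1 lists "Non-triple-negative breast cancer" with no visible qualifier beside it. The prior-treatment rule in Section 4.1 is "Refractory to or relapsed after at least one prior standard therapeutic regimen". The synopsis words it as relapse after a regimen, or that patients "were refractory to at least one standard chemotherapy (or biological, targeted or hormonal) regimen for their disease", so hormonal therapy is one way to qualify and not a condition. Section 10.4 plans response rate and response duration by indication.

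**SAP.** Section 1 announces results for the "metastatic non-triple-negative Breast Cancer (mBC) population" and refers to Section 4 for its definition. Section 4 gives it: "Metastatic, non-triple-negative breast cancer (mBC) Population: This will include all patients with hormone receptor-positive/human epidermal growth factor receptor 2-negative (HR+/HER2-) metastatic breast cancer" and, further, "who progressed on at least 1 prior hormonal therapy in the metastatic setting", with at least one dose at 10 mg/kg. Section 4.2 repeats the broad name for the safety population and points back to Section 4. Section 4 states that this population was added with version 3.0.

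**The concern.** Two documents for one study use the same name and abbreviation for two different sets of patients. Someone who knows the Protocol's cohort and then reads mBC response or survival results could take them as results for that cohort. They would be results for one receptor subtype with a particular treatment history.

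Two things are at stake. The first is interpretation: the label covers more than the population does. The second is completeness: by-indication efficacy reporting, which the Protocol calls for, would not cover every treated patient in one of its five main expansion cohorts. The timing makes transparency more important. The narrower definition came with SAP version 3.0 (1 February 2019), after the last patient enrolled on 22 June 2017, in an open-label study in which SAP Section 9 says administrative interim analyses had already been done.

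**Working it through.** No power, alpha or sample-size figure bears on this point, and SAP Section 6 plans no hypothesis test. The check is a comparison of definitions, followed by a search for where the excluded patients would be summarised.

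**Step 1: set the definitions side by side.**

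| Element | Protocol (visible text) | SAP Section 4 |
|---|---|---|
| Name | Non-triple-negative breast cancer, mBC (Section 3) | Same name and abbreviation |
| Receptor status | Any breast cancer that is not triple-negative (synopsis, Sections 3 and 4.1) | HR+/HER2- only |
| Prior treatment | One standard regimen of any kind (synopsis, Section 4.1) | Progression on hormonal treatment for metastatic disease |
| Dose | 10 mg/kg in the ongoing Phase II | At least one dose at 10 mg/kg |

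The dose condition matches the Protocol's ongoing Phase II. The other two conditions are additional.

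**Step 2: identify who falls between the definitions.** Within the treated 10 mg/kg non-TNBC patients, the SAP definition leaves out:
- HER2-positive patients; and
- HR+/HER2- patients whose disease had not progressed on hormonal treatment in the metastatic setting, for example those who had it only as adjuvant treatment.

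Both kinds of patient could enter under the visible Protocol rules.

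**Step 3: look for their efficacy results.** SAP Sections 5 and 6 and Table 2 assign efficacy to Target mTNBC, mBC, mUC, SCLC, NSCLC, CRC, EGC, EMC and PDC. None of these takes in the patients from Step 2. They do belong to the Overall Safety Population, but Table 2 leaves the efficacy row blank for it. Section 5 plans listings of all data for that population, but a listing is not a summary of ORR, DOR or PFS.

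**Step 4: look for their safety results.** SAP Section 7.1 plans the overall adverse-event summary, and events by organ class and preferred term, split by the tumour type recorded on the eligibility form. This covers the Overall Safety Population, where numbers are judged sufficient. Sections 5.2.1 and 5.5 extend demographics and exposure to the Section 7.1 subgroups. These subgroups do not carry the HR+/HER2- or hormonal-therapy conditions, so safety is at least partly covered.

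**Step 5: compare with the SAP's other populations.** The mUC population carries the Protocol's own prior-treatment rule. The SCLC, NSCLC, CRC, EGC, EMC and PDC populations are tied to the eligibility criteria as enrolled. The triple-negative population is also narrower than its Protocol cohort, but the word Target in its name signals this. Only the mBC population adds receptor and treatment-history conditions while keeping the Protocol's unqualified cohort name.

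**Step 6: ask how many patients are affected.** Neither document gives the number of non-TNBC patients treated, their receptor status or their hormonal-therapy history. The figure of 150 is a ceiling and not an enrolled number. No count, and no shift in ORR, can be derived.

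**The case against.** The strongest reply is that the SAP conceals nothing. The restriction stands in the same sentence as the label, Sections 1 and 4.2 refer the reader to it, and most later sections simply say mBC Population. Defined subsets are normal in this SAP, as Target mTNBC shows. The SAP also leaves several other Protocol tumour types, such as ovarian and prostate cancer, without a named efficacy population, so it does not claim to report every indication. All of this stands. It makes the problem one of label and scope, but it does not remove the conflict with the Protocol's use of the same term.

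Redaction and versions also matter. Text is blacked out after the prior-treatment rule in the synopsis and after the tumour list in Protocol 4.1, and the contents of SAP Section 11, on changes from the Protocol, are redacted. The bars inside the 4.1 list stand beside other tumour types and not beside non-TNBC. The SAP cites the Protocol of 24 April 2017 with Amendments 1 to 11, whereas the Protocol reviewed here includes Amendments 1 to 13. An explanation, or an earlier entry restriction, is possible.

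A reader might infer four stronger things, none of which the documents support:
- **That safety results for the cohort are also lost.** SAP 7.1 already plans adverse-event summaries by tumour type.
- **That patients have certainly been dropped, or that the reported ORR is inflated by some amount.** No counts or response rates are given, and the excluded number could be zero.
- **That the definition was chosen after seeing results.** The late date and the open-label design call for disclosure, but they are not evidence of selection.
- **That every output will carry a non-triple-negative heading.** No table shells are shown, and Table 2 heads its column only mBC.

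**Conclusion.** The point holds as a mismatch between label and population, with a consequence for efficacy reporting. On the visible text, the SAP's mBC population is by definition a subset of the Protocol's mBC cohort. Any treated non-TNBC patient outside it has no visible cancer-specific efficacy summary, contrary to the by-indication reporting in Protocol 10.4. Efficacy described as non-TNBC would apply to HR+/HER2- patients after progression on hormonal therapy, not to the cohort as enrolled.

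No magnitude is stated, because none can be. The conclusion rests on two assumptions: that the redacted passages contain no matching entry restriction or additional efficacy analysis, and that the Protocol version on which the SAP was written used the term as the present one does. If every treated 10 mg/kg non-TNBC patient in fact met the SAP definition, the two groups would coincide at that dose and only the label would need correcting.

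**What to change.** 1. Rename the SAP population to say what it is, for example HR+/HER2- metastatic breast cancer with progression on hormonal therapy, wherever it is now called non-triple-negative (Sections 1, 4 and 4.2, and any output titles).
2. Report how many treated 10 mg/kg non-TNBC patients fall outside that population, by reason: receptor status or hormonal-therapy history. If there are none, one sentence saying so closes the point.
3. If there are any, add descriptive ORR, DOR and PFS for all treated 10 mg/kg non-TNBC patients, using the methods already in SAP Section 6, and state that the narrower population was defined in version 3.0 after enrolment closed.

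The cost is one label change and, if needed, one extra set of descriptive outputs. The response and progression data are already collected under the Protocol, and no change to study conduct is required.
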